Appendix 1 Schedule of Activities (cont.)

Table 1 Arm A: Cobimetinib Plus Atezolizumab Schedule of Assessments (28-Day Cycles)

ADA=anti-drug antibody; Discon=discontinuation; ECHO=echocardiogram; ECOG=Eastern Cooperative Oncology Group; eCRF=electronic Case Report Form; EORTC QLQ-C30=European Organisation for Research and Treatment of Cancer Quality of Life Core 30 Questionnaire; EQ-5D-5L=European Quality of Life 5-Dimension, 5-Level questionnaire; FU=follow-up; HBcAb=hepatitis B core antibody; HBsAg=hepatitis B surface antigen; HBV=hepatitis B virus; HCV=hepatitis C virus; IRR=infusion-related reaction; LVEF=left ventricular ejection fraction; MUGA=multiple-gated acquisition; PK=pharmacokinetic; PO=by mouth; PRO=patient-reported outcome; RECIST v1.1=Response Evaluation Criteria in Solid Tumors, Version 1.1; T3=triiodothyronine; T4=thyroxine; Tx=treatment; WGS=whole genome sequencing.

Notes: All assessments should be performed within ± 3 days of the scheduled visit, unless otherwise specified. On treatment days, all assessments should be performed prior to dosing, unless otherwise specified. On treatment days, pre-infusion laboratory samples should be drawn 0–4 hours before the start of infusion, and post-infusion laboratory samples should be drawn 0–30 minutes after the end of infusion, unless otherwise specified. Assessments shaded in gray should be performed as scheduled, but the associated data do not need to be recorded on the eCRF (except in the case of an adverse event).

- ^a Perform screening tests within 35 days prior to treatment initiation (Day 1) unless the patient meets criteria specified in Section 4.5.1. Standard-of-care screening assessments may be performed concurrently with *BRAF*^{V600} mutation and PD-L1 testing. *BRAF*^{V600} status must be known prior to performing study-specific screening assessments. The 35-day window begins at the time of the first standard-of-care screening assessment or the first study-specific screening assessment after the *BRAF*^{V600} mutation test result is available, whichever is earlier. Results of standard-of-care tests or examinations performed prior to obtaining informed consent and within 35 days prior to treatment initiation (Day 1) may be used; such tests do not need to be repeated for screening. For a list of laboratory tests for which results must be obtained within 14 days prior to the first dose of study drug, see Section 4.1.1.2. Test results should be reviewed prior to administration of study drug. PD-L1 will be assessed by central laboratory and the result will be used for stratification and randomization only.
- ^b Patients who discontinue study drug will return to the clinic for a treatment discontinuation visit within 30 (+7) days. The visit at which response assessment shows progressive disease may be used as the study discontinuation visit.
- ^c Required follow-up information will be collected via telephone calls and/or clinic visits every 3 months until death, loss to follow-up, or study termination by the Sponsor.
- ^d Day 1 of Cycle 1 can occur up to 3 days after randomization.
- ^e Visit not specified by the protocol. Assessments (possibly including PK sample collection) should be performed as clinically indicated.
- ^f Informed consent must be documented before any study-specific screening procedure is performed and may be obtained up to 35 days before initiation of study treatment.
- ^g Vital signs include respiratory rate, pulse rate, and systolic and diastolic blood pressure while the patient is in a seated position, and temperature. Resting oxygen saturation will be measured during screening and subsequent visits. Record abnormalities observed at baseline on the General Medical History and Baseline Conditions eCRF. At subsequent visits, record new or worsened clinically significant abnormalities on the Adverse Event eCRF.
- ^h At the first atezolizumab infusion, vital signs will be recorded within 60 minutes prior to the infusion, every 15 (± 5) minutes during the atezolizumab infusion, and 30 (± 10) minutes after the infusion if clinically indicated. For subsequent infusions, vital signs will be collected within 60 minutes prior to the infusion and, if the patient experienced an infusion-related reaction with the previous infusion or if clinically indicated, vital signs should be collected during the infusion and 30 (± 10) minutes after the infusion.

Appendix 1 Schedule of Activities (cont.)

Table 1 Arm A: Cobimetinib Plus Atezolizumab Schedule of Assessments (28-Day Cycles)

-
- ⁱ Perform a limited, symptom-directed examination at specified timepoints or as clinically indicated. Record new or worsened clinically significant abnormalities on the Adverse Event eCRF. If physical examinations are assessed within 7 days of the Day 1, Cycle 1 visit, they do not have to be repeated on Day 1.
- ^j Hematology includes WBC count, RBC count, hemoglobin, hematocrit, reticulocyte count, platelet count, and differential count (neutrophils, bands, eosinophils, basophils, monocytes, and lymphocytes)
- ^k Chemistry panel (serum) includes sodium, potassium, chloride, bicarbonate or total CO₂ (HCO₃ and CO₂ not mandatory if unavailable at site), glucose, BUN or urea, creatinine, albumin, magnesium, phosphorus, calcium, total and direct bilirubin, ALP, ALT, AST, CPK, uric acid, LDH, and total protein. Fasting triglycerides, fasting cholesterol, fasting LDL cholesterol, and fasting glucose will be assessed after a minimum 8-hour fast for screening only. Non-fasting laboratory values will be accepted for subsequent visits after screening. If fasting laboratory values are clinically warranted in a subject, then it will be at the discretion of the investigator. LDH will be assessed by both local and central laboratory, and the central laboratory result will be used for stratification and randomization only.
- ^l All patients will undergo evaluation of left ventricular dysfunction, either by ECHO or MUGA, at screening. Evaluation of LVEF by ECHO or MUGA scan must be performed at the following timepoints only for patients randomized to receive cobimetinib:
- Day 1 of Cycle 2 (± 1 week).
 - Day 1 of Cycles 5, 8, 11, 14, 17, etc. (every three treatment cycles; ± 2 weeks).
 - Treatment discontinuation visit evaluation of LVEF does not need to be performed at treatment discontinuation visit if an evaluation has been performed within the last 12 weeks and there are no clinically significant findings and/or changes from baseline.
- ^m Tumor assessments will be performed every 8 weeks (± 1 week) from the date of first study drug administration (Day 1) through 18 months (80 weeks) and then every 12 weeks (± 1 week) thereafter. Refer to Section 4.5.5.
- ⁿ Tumor assessments will continue until disease progression per RECIST v1.1, loss of clinical benefit (for patients who continue treatment after disease progression according to RECIST v1.1) (see Section 3.1.2), withdrawal of consent, study termination by the Sponsor, or death, whichever occurs first. Patients who discontinue treatment for reasons other than disease progression (e.g., toxicity) will continue scheduled tumor assessments until disease progression, withdrawal of consent, study termination by Sponsor, or death, whichever occurs first. A confirmatory scan will be needed 4–8 weeks after progression of disease to confirm progression and exclude pseudoprogression. Refer to Section 4.5.5 for details.
- ^o All patients will be tested for HIV prior to the inclusion into the study and HIV-positive patients will be excluded from the study. HBV serology will include HBsAg, antibodies against HBsAg, total anti-HBcAb. HBV DNA should be obtained prior to randomization if patient has a negative serology for HBsAg and a positive serology for anti-HBcAb. HCV serology will include HCV antibody (anti-HCV). HCV RNA should be obtained prior to randomization if patient tests positive for anti-HCV.
- ^p Thyroid-function testing (thyroid-stimulating hormone, free T3 [or total T3 for sites where free T3 is not performed], and free T4) collected on Day 1 of Cycles 1–5, and every second cycle thereafter (e.g., Day 1 of Cycles 7, 9, 11, etc).

Appendix 1 Schedule of Activities (cont.)

Table 1 Arm A: Cobimetinib Plus Atezolizumab Schedule of Assessments (28-Day Cycles)

- ^q All patients will undergo ophthalmologic examination (see Section 4.5.10 for exam requirements) at screening. Ophthalmologic examination must be performed at the following timepoints only for patients randomized to receive cobimetinib:
- Day 1 of Cycle 2 (± 1 week).
 - Day 1 of Cycles 5, 8, and 11 (every three treatment cycles; ± 2 weeks).
 - Day 1 of Cycles 15, 19, and 23 (every four treatment cycles; ± 2 weeks).
 - Day 1 of Cycles 29, 35, 41, 47, etc. (every six treatment cycles; ± 2 weeks).
 - Treatment discontinuation visit.
- ^r All women of childbearing potential will have a serum pregnancy test at screening within 7 days prior to Day 1 of Cycle 1. Urine pregnancy tests will be performed on Day 1 of every cycle, at the treatment discontinuation visit, and 3 months after cobimetinib discontinuation and 5 months after atezolizumab discontinuation. If a urine pregnancy test is positive, it must be confirmed by a serum pregnancy test.
- ^s Includes dipstick (pH, specific gravity, glucose, protein, ketones, and blood), and microscopic examination (sediment, RBCs, WBCs, casts, crystals, epithelial cells, and bacteria).
- ^t Includes any medication (e.g., prescription drugs, over-the-counter drugs, herbal or homeopathic remedies, nutritional supplements) used by a patient from 7 days prior to initiation of study drug until 30 days after the last dose of study drug.
- ^u After informed consent has been obtained but prior to initiation of study drug, only serious adverse events caused by a protocol-mandated intervention should be reported. After initiation of study drug, all adverse events will be reported until 135 days after the last dose of study drug or initiation of new anti-cancer therapy, whichever occurs first. After this period, all deaths, regardless of cause, should be reported (per Section 5.3.5.8). After this period, the Sponsor should be notified if the investigator becomes aware of any serious adverse event that is believed to be related to prior study drug treatment (see Section 5.6). The investigator should follow each adverse event until the event has resolved to baseline grade or better, the event is assessed as stable by the investigator, the patient is lost to follow-up, or the patient withdraws consent. Every effort should be made to follow all serious adverse events or adverse events of special interest considered to be related to study drug or trial-related procedures until a final outcome can be reported.
- ^v Archival tumor tissue with sample collection date < 5 years or fresh baseline tumor tissue will be collected during screening. An optional on-treatment biopsy will be obtained at Cycle 1, Day 15 (± 5 days), and a mandatory biopsy will be obtained at progression if clinically feasible.
- ^w PRO instruments, the EORTC QLQ-C30 and EQ-5D-5L, will be completed in this order using an electronic device on Day 1 of Cycle 1 and every 4 weeks (± 3 days) thereafter, prior to tumor assessments visits every 8 weeks, at the treatment discontinuation visit, and at unscheduled visits, as clinically indicated. Patients will also complete the questionnaires every 4 weeks for 6 months after treatment discontinuation. All PRO questionnaires are required to be completed prior to the administration of study treatment and/or prior to any other study assessment(s) that could bias a patient's responses.
- ^x The initial dose will be delivered over 60 (± 15) minutes. If the first infusion is well tolerated all subsequent infusions will be delivered over 30 (± 10) minutes until loss of clinical benefit. Study drug administration may be ± 3 days after the first cycle.
- ^y Medication diaries should be collected and reviewed and unused medications should be collected for assessment of compliance.

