4.3.2.2 Atezolizumab

Patients randomized to Arm A will receive atezolizumab 840 mg by IV infusion on Day 1 and Day 15 of each 28-day cycle. This 4-week period is considered a treatment cycle.

Atezolizumab will be administered in a monitored setting where there is immediate access to trained personnel and adequate equipment and medicine to manage potentially serious reactions.

For more detailed information on drug preparation, storage, and administration, refer to the Atezolizumab Investigator's Brochure and pharmacy manual.

Atezolizumab infusions will be administered per the instructions outlined in [Table 2](#).

Table 2 Administration of First and Subsequent Infusions of Atezolizumab

First Infusion	Subsequent Infusions

• No premedication is permitted prior to the atezolizumab infusion.• Vital signs (pulse rate, respiratory rate, blood pressure, and temperature) should be recorded within 60 minutes prior to the infusion.• Atezolizumab should be infused over 60 (\pm 15) minutes.• If clinically indicated, vital signs should be recorded during the infusion at 15, 30, 45, and 60 minutes (\pm 5 minutes for all timepoints) during the infusion and at 30 (\pm 10) minutes after the infusion.• Patients should be informed about the possibility of delayed post-infusion symptoms and instructed to contact their study physician if they develop such symptoms.	
• If the patient experienced an infusion-related reaction with any previous infusion, premedication with antihistamines, antipyretics, and/or analgesics may be administered for subsequent doses at the discretion of the investigator.• Vital signs should be recorded within 60 minutes prior to the infusion.• Atezolizumab should be infused over 30 (\pm 10) minutes if the previous infusion was tolerated without an infusion-related reaction, or 60 (\pm 15) minutes if the patient experienced an infusion-related reaction with the previous infusion.• If the patient experienced an infusion-related reaction with the previous infusion or if clinically indicated, vital signs should be recorded during the infusion and at 30 (\pm 10) minutes after the infusion.

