Dose modifications to atezolizumab are not permitted. Guidelines for treatment interruption or discontinuation and the management of specific adverse events are provided in Section [5.1.5](#), [Appendix 10](#) (cobimetinib plus atezolizumab-associated AE management), [Appendix 11](#) (atezolizumab-associated AE management).

For anaphylaxis precautions, see [Appendix 7](#).

See the pharmacy manual for detailed instructions on drug preparation, storage, and administration or guidelines for dosage modification and treatment interruption or discontinuation are provided in Section [5.1.5.2](#), [Appendix 10](#), and [Appendix 11](#).

Any overdose or incorrect administration of study drug should be noted on the Study Drug Administration eCRF. Adverse events associated with an overdose or incorrect administration of study drug should be recorded on the Adverse Event eCRF (see Section 5.4.4).

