4.5.4 Vital Signs

Vital signs will include temperature (measured in degrees Centigrade), pulse rate, respiratory rate, and systolic and diastolic blood pressure while the patient is in a seated position. Blood pressure and pulse rate measurements will be recorded after a 5-minute rest while the patient is in a seated position. Resting oxygen saturation will be measured during screening and at subsequent visits.

Vital signs will be measured and recorded at the following timepoints:

- Within 60 minutes prior to infusion
- During infusion or after infusion per schedule of assessments

For patients who experienced an infusion-related reaction (IRR) during the previous atezolizumab infusion, refer to Section 4.3.2.2. For patients who experienced an IRR during the previous pembrolizumab infusion, refer to the prescribing information for pembrolizumab.

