Appendix 1 Schedule of Activities (cont.)

Table 1 Arm A: Cobimetinib Plus Atezolizumab Schedule of Assessments (28-Day Cycles)

Assessment/Procedure (Visit Window in Days)	Screen ^a	Cycle 1		Cycle 2		Cycles ≥ 3		Tx Discon ^b	Unscheduled Visit ^e	Survival FU ^c	
	Days -35 to -1	Day 1 (+3) ^d	Day 15 (±3)	Day 1 (±3)	Day 15 (±3)	Day 1 (±3)	Day 15 (±3)	< 30 Days after Last Dose (+7)		Every 3 Months	
ECHO or MUGA scan ^l	x			x ^l		x ^l		x ^l			
12-Lead ECG	x	As clinically indicated									
Optional WGS sample		x									
Tumor assessments	x	Scans will be performed every 8 or 12 weeks ^{m, n}									
Serology ^o	x										
Thyroid function ^p	x	x		x		x ^p		x			
Ophthalmologic exam ^q	x			x		x ^q		x			
Pregnancy test ^r	x	x ^r		x ^r		x ^r		x ^r			
Urinalysis ^s	x										
Concomitant medications ^t	x ^t	x ^t		x		x		x ^t	x		
Adverse events ^u	x ^u	x ^u	x	x	x	x	x	x ^u	x	x ^u	
Tumor biopsy ^v	x		x					x			
EORTC QLQ-C30 and EQ-5D-5L ^w		x		see Footnote ^w				x ^w	x		
Biomarker blood samples		See Appendix 2							x		
Atezolizumab administration ^x		x	x	x	x	x	x				
Cobimetinib accountability ^y		x		x		x		x			
Dispense cobimetinib ^z		x		x		x					
Survival and anti-cancer therapy FU										x ^{aa}	

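### The schedule footnote keeps atezolizumab infusions at 30 minutes after a late infusion-related reaction, where the dosing section calls for 60

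*Protocol*

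**What the plan says.** In Appendix 1, Table 1 (the Arm A schedule), the row "Atezolizumab administration ^x" carries footnote x. After setting the initial dose at 60 (±15) minutes, the footnote continues: "If the first infusion is well tolerated all subsequent infusions will be delivered over 30" (±10) minutes, to run until loss of clinical benefit. It contains no exception and no cross-reference. SAP Appendix 2 reproduces the same footnote.

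Section 4.3.2.2 says: "Atezolizumab infusions will be administered per the instructions outlined in" Table 2. For infusions after the first, Table 2 has two branches. When the one before passed without a reaction, the duration is 30 (±10) minutes. The longer duration, 60 (±15), has its own condition, worded as follows: "minutes if the patient experienced an infusion-related reaction with the previous infusion".

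Three other places bear on the point:

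- Section 4.5.4 (Vital Signs): "For patients who experienced an infusion-related reaction (IRR) during the previous atezolizumab infusion, refer to Section 4.3.2.2".
- Footnote h of the same Appendix 1 table makes vital signs during and after later infusions conditional: "if the patient experienced an infusion-related reaction with the previous infusion or if clinically indicated".
- Section 4.3.2.2 also sends sites elsewhere: "See the pharmacy manual for detailed instructions on drug preparation, storage, and administration". It names the Atezolizumab Investigator's Brochure for administration as well. Neither document is available here.

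**The concern.** The two rules turn on different events. Footnote x looks once, at the first infusion, and fixes every later duration from it. Table 2 looks at the immediately preceding infusion each time. They agree for a patient who never reacts. They part for a patient who tolerates the first infusion, reacts at a later one and stays on treatment.

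For that patient's next infusion, a site working from the schedule would give atezolizumab faster than the dosing section intends, directly after a reaction. A site working from Table 2 would depart from the schedule. What is at stake is a clear and cautious instruction for a small group of Arm A patients. No endpoint, data item or analysis depends on it.

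**Working it through.** The documents state no derived figure to reproduce. The check compares the two texts and then works out the time windows.

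**Inputs.** Dose 840 mg (Section 4.3.2.2). Footnote x: 30 (±10) minutes. Table 2 after a reaction: 60 (±15) minutes.

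**Test case.** Infusion 1 is tolerated, infusion 2 causes a reaction, and infusion 3 is due.

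| | Footnote x | Table 2 |
|---|---|---|
| Deciding event | Infusion 1, tolerated | Infusion 2, reaction |
| Window for infusion 3 | 30 − 10 = 20 to 30 + 10 = 40 min | 60 − 15 = 45 to 60 + 15 = 75 min |
| Rate at the window limits | 840/40 = 21.0 to 840/20 = 42.0 mg/min | 840/75 = 11.2 to 840/45 = 18.7 mg/min |
| Nominal rate | 840/30 = 28 mg/min | 840/60 = 14 mg/min |

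The windows are 45 − 40 = 5 minutes apart, so no duration satisfies both rules. The slowest rate under footnote x (21.0 mg/min) exceeds the fastest under Table 2 (18.7 mg/min). The rates restate the time windows; they do not measure risk.

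**Which rule governs.** Section 4.3.2.2 names Table 2 as the instruction for atezolizumab infusions, and that is sufficient.

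**Whether the omission is a convention of the schedule.** It is not. Footnote h of the same table carries the previous-infusion condition for vital signs; footnote x does not carry it for duration.

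**Whether Appendix 11, Table 7 fills the gap.** It does not.

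- Grade 1, and Grade 2 that resolves: treatment may continue. For later infusions the table mentions premedication and close monitoring, not duration.
- Grades 3 and 4, and Grade 2 with no improvement within 24 hours: atezolizumab is permanently discontinued, so these patients are outside the conflict unless re-challenge is approved.
- Footnote e of Table 7 mentions a longer infusion time, but only as an option at approved re-challenge.

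**Extent.** Under Table 2 the duration returns to 30 (±10) minutes once an infusion is tolerated, so each late reaction creates a conflict for the next infusion only. Footnote x also gives no duration for later infusions when the first is not tolerated; Table 2 covers that case.

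**The case against.** The strongest reply is that no patient lacks a correct instruction. The dosing section states the 60-minute rule explicitly, and Appendix 1 is a schedule of activities whose footnote can be read as shorthand for the usual course. Harm would need a tolerated first infusion, a later mild or resolving reaction, continued treatment, and a site that follows the schedule instead of Section 4.3.2.2. The documents give no frequency for that sequence. For a Grade 1 reaction, Table 7 itself lets the rate return to the original within the same infusion after 30 tolerated minutes at half rate, so the protocol does not treat the faster rate as unacceptable in a patient who has just reacted. The pharmacy manual or the Investigator's Brochure may state the right rule where the drug is prepared and given. Finally, the pointer in Section 4.5.4 sits among vital-sign instructions and does not settle which duration prevails.

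Most of this stands, and it limits the importance of the point. The safety consequence is possible, not shown, and Section 4.5.4 is at best supporting evidence. The shorthand reading does not stand: the footnote covers all later infusions up to loss of clinical benefit, which leaves no room for an unstated exception, and it does not refer the reader to Table 2.

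**Conclusion.** The inconsistency holds. Footnote x states the wrong duration for the infusion that follows a reaction occurring after a tolerated first infusion: 20–40 minutes where the governing table gives 45–75, with no overlap and in the less cautious direction. It is minor. It reaches only patients who continue after a late Grade 1 or resolving Grade 2 reaction (or who are re-challenged with approval), and only their next infusion.

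The textual conflict is certain. Its clinical effect is not known, because the documents report neither how often reactions first occur after infusion 1 nor any link between infusion time and repeat reactions. Which source a site would follow also depends on manuals not seen here. No statistical quantity is affected.

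**What to change.** In protocol Appendix 1, Table 1, footnote x, replace only the second sentence so that duration depends on the preceding infusion and Table 2 is cited. Suggested wording: *Later infusions: 30 (±10) minutes when the preceding one caused no infusion-related reaction, and 60 (±15) minutes when it did (see Section 4.3.2.2, Table 2); continue until loss of clinical benefit.* Keep the sentences on the initial dose and the ±3-day window. A bare cross-reference to Table 2 would also work and would avoid stating the rule twice. Aligning the copy in SAP Appendix 2 is optional, since the SAP does not govern dosing.

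The cost is one sentence, with no effect on data collection or analysis. Section 9.6 requires ethics approval, and regulatory approval where local rules ask for it, before a change is implemented. SAP Section 2.5 says the study will be terminated early. The correction therefore belongs in a further amendment if there is one, and does not justify an amendment of its own.
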